Success Criteria: Actively participate in the data sharing consortium, and adopt best practices/efforts to comply with the recommendations of the data sharing consortium, throughout all years and/or stages of the award.

Rationale: Participation and maintaining an active membership status in the consortium is a requirement of the RFA.

Milestone 1.2: Obtain FDA IDE for the use of the Boston Scientific Vercise DBS system with their novel directional lead.

Success Criteria:	A full approval letter from FDA, obtained in collaboration with Boston Scientific, with no major study design considerations. A copy of the FDA approval letter will be sent to the NIH Project Officer. All correspondence from FDA regarding the IDE will be shared with the NIH Project Officer within 30 days of receipt.
Rationale:	The IDE is required for study initiation. Boston Scientific's regulatory staff estimates that the IDE can be obtained within 6 to 9 months. Any major study design consideration will be considered and resolved to maximize the probability that a future pivotal study can proceed with the data collected in this feasibility study.
Milestone 1.3:	Obtain IRB approvals of final clinical study as approved by FDA and register the study on www.clinicaltrials.gov.
Success Criteria:	Documentation of full approval from the UAB IRB, along with registration on clinicaltrials.gov. IRB approval and informed consent documents will be shared with the NIH Project Officer.
Rationale:	Maintaining IRB approval is a requirement for a clinical study as is registering the study on www.clinicaltrials.gov .
Milestone 1.4:	Safety Monitoring Committee will meet to discuss all AEs and SAEs at the end of Y1.
Success Criteria:	The SMC will include a biostatistician, and neurosurgeon, and a neurologist. Meeting proceedings and decisions will be communicated to the PI and to the NIH Project Officer.
Rationale:	This process will ensure ongoing safety of the study.
Milestone 1.5:	Participant enrollment follows approved protocol.
Success Criteria:	All subjects follow research protocol as summarized in Error! Reference source not found. and Error! Reference source not found. Follow-up at 1 year post-crossover completion with ≥80% of the participants.

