SA1. To test the hypothesis that specific contacts on a novel segmented DBS lead in the STN region activate functionally distinct populations of cortical axons within individual PD patients. SA1.1 will measure within-participant contrasts in therapeutic window and UPDRS part 3 change versus pre-op baseline across the different segments on the directional DBS lead with two-way repeated measures mixed models using Proc Mixed in SAS, with conventional versus current steering DBS contacts as factors and therapeutic window and change in UPDRS part 3 as data. The primary outcome measure for SA1.2 will compare whether intraoperative ERPs predict within-participant changes in the clinical outcomes from SA1.1. We will contrast the ERPs within and across stimulation sites with two-way repeated measures mixed models using Proc Mixed in SAS, with stimulus amplitude, location, and recording modality (EEG or ECOG) as factors and P1/N1 latency and HFO integrated area as data. Using linear contrasts from the regressions, we will directly compare whether EEG and ECOG measures of DBS amplitude thresholds (1) that change P1/N1 latency and (2) elicit the large amplitude HFOs better predict the size of the therapeutic window for a given DBS electrode contact. Secondary outcomes will correlate these amplitude thresholds with changes in the UPDRS part 3 score, UPDRS subscores, and other elements of the Motor battery measured in SA1.1. To control for potential subclinical corticospinal tract activation, we will report the latency and magnitude of EMG response(s) in the contralateral arm and leg muscles using residual analyses, when and if these responses are present. Sample size for SA1. Our preliminary findings show robust within- and between-subject changes in ERP latency that predict postoperative motor side effects. For the first primary outcome, a sample size of 18 will have 80% power to detect a difference between a null hypothesis regression slope of 0 and an alternative regression slope of 0.3 or higher standardized units, assuming that the standard deviation of the predictor variable, DBS amplitude threshold, is 2.370 mA (the standard deviation of the stimulus intensities) and the standard deviation of the normalized residuals ($sd=1$) of the therapeutic window using a t-test with a 0.05 two-sided significance level. Thus, we will be overpowered for SA1, because a large sample of 30 is dictated by SA2.3. As an additional secondary analysis, we will compare the predictive power of EEG versus ECOG, we will first regress the primary outcomes on EEG and then determine how much of the residual variance is explained by ECOG. If EEG explains 50% of the variance in the primary outcome, then we will have 80% power to detect an increase in the R-square of 8.6%. If the additive R-square of EEG is 25%, we will have 80% power to detect an increase of 12.9%. If we cannot demonstrate superiority of ECOG, we would default to the less invasive modality. We will look at the assumptions of the model by examining the residual plots in the regression models for both modalities.

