selected based cortical ERP physiology, using both therapeutic window and change in UPDRS part 3 as data nested within person. Secondary analyses will contrast the efficacy of these DBS adjustment strategies based upon changes in other elements of the Motor battery. In SA 2.3, we use the randomized, doubleblind crossover trial to compare changes in UPDRS and other measures of quality of life and motor, cognitive, behavioral, and speech function across the DBS programming strategies identified in SA 2.1. The primary statistical analysis will use Proc Mixed in SAS with active contact groupings including (1) conventional DBS, (2) multiple active contacts selected based on behavior, and (3) multiple active contacts based on ERPs as factor and patient preference and changes in PDQ-39 and UPDRS part 3 as data. Sample size for SA2. We will obtain multiple repeated measures within participants and can readily detect changes in patient preference, PDQ-39, UPDRS part 3, and other motor and non-motor variables of interest. Patient reported evidence for the hypothesis of superiority of current steering will be shown by determining that 20 or more of the 30 participants favor either current steering approach over conventional DBS using a binomial distribution based on patient preference (vote), PDQ-39, and UPDRS part 3. This would achieve a p value of < 0.049 . We will declare current steering DBS to be clinically superior to conventional therapy based on patient preference if 20 or more patients meet this criterion. We will measure the frequency by which current steering provides better outcomes versus conventional DBS, which could still be highly relevant and significant clinically (even if preferred by <20 participants). Secondary measures will quantify within-participant changes in upper limb dexterity, gait speed test, posture and balance, cognitive/behavioral measures, speech, and motor diaries. Additionally, we will contrast the probability that active contacts are shared among the programming strategies (conventional DBS, current steering guided by behavior, and current steering guided by cortical physiology). The extent to which contacts and stimulation parameters are shared among these approaches could be informative and provide a useful internal validation of the current steering approach.

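### The 20-of-30 superiority rule counts a vote for either of two steering approaches but takes its p value from a null of 1/2; if the vote is the three-way ranking, the null is about 2/3 and the rule can fire 58% of the time with no true difference

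*SAP*

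**What the plan says.** SA 2.3 compares three programming strategies: conventional DBS, steering contacts chosen by behavioural testing, and steering contacts chosen by ERPs. The primary model is Proc Mixed, with "multiple active contacts based on ERPs as factor and patient preference and changes in PDQ-39 and UPDRS part 3 as data".

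The SAP paragraph headed Sample size for SA2 then adds a separate counting rule. Evidence for steering is that "20 or more of the 30 participants favor either current steering approach over conventional DBS using a binomial distribution", and the sentence continues "based on patient preference (vote), PDQ-39, and UPDRS part 3". It goes on: "This would achieve a p value of < 0.049". The declaration follows: "We will declare current steering DBS to be clinically superior to conventional therapy based on patient preference if 20 or more patients meet this criterion". Neither the null proportion, nor the sidedness, nor the handling of ties is given.

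The Sample size for SA1 paragraph says that "a large sample of 30 is dictated by SA2.3". Protocol item 16a (Crossover Study and Exploratory Crossover Arm) collects preference by asking participants at study conclusion to rank the strategies from best to worst.

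**The concern.** A null of 1/2 belongs to one comparison between two options. Here a participant counts as a success if at least one of two steering approaches beats conventional DBS. Two of the three options lead to success, so chance alone favours steering. If the per-patient null exceeds 1/2, the stated p value understates the false-positive rate.

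This is the SAP's only stated rule for declaring steering superior, and it is the numerical basis given for the 30 participants in SA 2.3. The rationale to Protocol Milestone 1.2 wants design issues settled so that "a future pivotal study can proceed with the data collected in this feasibility study"; a false declaration could carry forward into that planning. The reach is limited to this declaration and its sample-size statement. The Proc Mixed analysis of SA 2.3 is not affected.

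**Working it through.** **Inputs.** Threshold 20, n = 30 and p < 0.049 (SAP, Sample size for SA2); three strategies, two of them steering (SAP, SA 2.3); vote collected as a ranking (Protocol 16a). Correlations, tie rates and true preference shares are not in the documents; those used below are assumptions.

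**1. Reproduce the stated figure.** P(X ≥ 20) for X ~ Binomial(30, 1/2) is 0.0494. This agrees with the stated 0.049 to three decimals, although it is not literally below it. The alternatives do not match: two-sided exact 0.0987; normal approximation 0.0339; normal with continuity correction 0.0502; null 1/3 gives 0.0002; null 2/3 gives 0.585. The null of 1/2 is therefore inferred, and the test is one-sided.

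**2. Null for the 'either' count.** A participant fails only if conventional DBS ranks first. With three exchangeable strategies and no ties that has probability 1/3, so the success probability is 2/3 and the expected count is 30 × 2/3 = 20. P(X ≥ 20) for Binomial(30, 2/3) is 0.585. Enumerating the ranking patterns gives the same value. The first threshold below one-sided 0.05 is 25 (0.0355); 24 gives 0.0838.

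**3. Correlated steering responses.** Assume normal responses with equal means and variances, conventional DBS independent, and correlation ρ between the two steering responses. Then P(conventional best) = 1/4 + asin((1 + ρ)/2)/(2π).

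| ρ | P(success) | P(X ≥ 20) |
|---|---|---|
| −0.5 | 0.710 | 0.769 |
| 0 | 0.667 | 0.585 |
| 0.25 | 0.643 | 0.473 |
| 0.5 | 0.615 | 0.352 |
| 0.75 | 0.580 | 0.222 |
| 0.9 | 0.551 | 0.136 |
| 1.0 | 0.500 | 0.049 |

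**4. No preference.** If a share t has no preference and does not count as favouring steering, the null is (1 − t) × 2/3. For t = 10%, 20% and 25% this is 0.600, 0.533 and 0.500, and the rule fires with probability 0.291, 0.099 and 0.049.

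**5. Two separate pairwise tests.** If each approach is tested against conventional DBS at 20/30, 1/2 is the right null for each. The exact joint distribution of the two counts then gives a 0.091 chance of at least one false declaration under exchangeable rankings and 0.074 at ρ = 0.9. It can never exceed 2 × 0.0494 = 0.0987.

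**6. All three measures required.** If vote, PDQ-39 and UPDRS part 3 must each favour steering (either approach on each, ρ = 0, simulated), between-measure correlations of 0, 0.3, 0.5, 0.7 and 0.9 give per-patient nulls of 0.296, 0.368, 0.419, 0.479 and 0.560. P(X ≥ 20) is then < 0.0001, 0.0009, 0.0055, 0.030 and 0.159.

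**The case against.** The strongest reply is that 58% describes one scenario. It needs a vote-only count, a vote taken from the three-way ranking, exchangeable rankings and no ties, and the SAP states none of these. If all three measures must agree, the error is 3% or less for between-measure correlations up to 0.7. This stands: even the direction of the error depends on a combination rule that is not written down. But the declaration sentence speaks of patient preference, which supports the vote-only reading, and the SAP's p value is not tied to any composite.

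Exchangeability is also not secured. The Crossover Study text in Protocol 16a randomises three conditions, while the Exploratory Crossover Arm text and Table 3 (16d) put the ERP-guided condition after a two-condition randomised crossover. A fixed last position could shift preference either way. So 2/3 is a reference value, not one guaranteed by the design.

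Protocol 16a does refer to primary outcomes comparing directional with omnidirectional DBS, and for that one pair 1/2 would be right. Neither that text nor Table 3 describes a two-way vote, however, and the SAP's wording covers both steering approaches.

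Overlap between the settings is plausible, since "we will contrast the probability that active contacts are shared among the programming strategies". Overlap implies positive correlation or ties, and both reduce the error. They restore 4.9% only if the two steering settings always stand or fall together, or if about a quarter of participants express no preference.

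Finally, the protocol's therapeutic-window milestones (2.4, 2.6, 4.3) do not use the 20/30 rule, and Milestone 1.2 does not make anything conditional on it. That limits the consequence but leaves the rule wrong.

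**Conclusion.** The concern holds, and the rule must be corrected before it is used. The stated p value belongs to one two-way comparison, and the rule as worded is not one. On the vote-only reading the false-positive rate is 58% with exchangeable rankings and no ties, and 14% to 47% for assumed correlations from 0.9 down to 0.25. On the two-test reading it is about 9%. The stated 4.9% returns only in the special cases above. On an all-three-measures reading the rule could instead be conservative, so as written it has no known error rate. Confidence is high that the stated level is unsupported; the exact size rests on the assumptions listed. The missing sidedness and tie handling are reporting gaps.

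**What to change.** Base the declaration on the preference vote alone and leave PDQ-39 and UPDRS part 3 to the Proc Mixed analysis. Replace the 'either' count with pairwise votes against conventional DBS, read from the ranking already collected, with null 1/2. Choose one of:

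- **(a)** one pre-specified pair, at 20/30 (one-sided 0.049) or 21/30 (two-sided 0.043);
- **(b)** both pairs, each at 21/30 (one-sided 0.021 each; 0.041 overall under exchangeable rankings, at most 0.043).

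Suggested text for (b):

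> A steering approach is declared superior on preference if at least 21 of 30 participants rank it above conventional DBS (exact binomial, null 1/2, one-sided). Ties count as not favouring steering.

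If fewer than 30 vote, (b) uses the exact one-sided 0.025 threshold: 20 of 28 (0.0178), 19 of 26 (0.0145) or 18 of 24 (0.0113). These are conservative if applied to (a) at 20/30. The same rule should be stated for more than 30 votes, since Protocol item 15a allows 40 participants.

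If the 'either' count is kept, test it against 2/3 at 25/30 (0.0355). That controls error only when the correlation is not negative; at ρ = −0.5 it is 0.094.

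State the sidedness. Before a primary pair is chosen, Protocol 16a, 16d with Table 3, and Milestone 2.6 must be reconciled on which conditions are randomised and double-blind. Then restate the SA2 sample-size paragraph.

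**Cost.** SAP wording only; no new data. For assumed true shares of 70%, 75% and 80% favouring an approach, pairwise power at 21/30 is 59%, 80% and 94%, against 73%, 89% and 97% at 20/30, so 30 remains workable. Keeping 'either' at 25/30 costs more: power is 43% at a true 80% and 71% at 85%. Reaching 80% power at a true 80% would need about 72 to 79 participants, against the planned enrolment of 40.

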During the Motor Battery assessments in the crossover, we will conduct Field Shaping Surveys to determine whether tailored activation of combinations of DBS contacts, guided by patient-specific network physiology, predicts changes in therapeutic window (the range of therapeutically effective stimulus amplitudes versus omnidirectional DBS). They will occur in the motor assessments at the conclusion of the first two crossover conditions. While in the operating room we will measure stimulus evoked activity and local field potential data through the DBS lead in response to hand, leg, and mouth movements. In addition to the primary study outcomes comparing directional versus omnidirectional DBS, we will use these encounters to determine if specific combinations of DBS contacts, guided by stimulus evoked activity and local field potentials in surgery, improve motor symptoms. Behavioral measures will include therapeutic window, MDS-UPDRS Part III, pegboard dexterity, gait speed test, and dynamic balance/posture measures (see motor battery above for descriptions) across different combinations of contacts on the segmented lead.

Non-motor assessments will occur on a different day and include patient-reported quality of life measures, cognitive/behavioral, and speech batteries (discussed previously). At study conclusion, we will conduct an open-ended exit interview to ask patients about their overall experience, to rank the programming strategies from the crossover study from best to worst, and explain their rationale for the rankings.

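### The 20-of-30 superiority rule names three outcomes under one p value without saying which decides; 0.049 holds only for a single one-sided count with a null of 1/2

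*SAP*

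**What the plan says.** The rule stands in the SAP, Statistical Analyses, under Sample size for SA2. Evidence of superiority is that "20 or more of the 30 participants favor either current steering approach over conventional DBS", judged "using a binomial distribution based on patient preference (vote), PDQ-39, and UPDRS part 3". One p value follows: "This would achieve a p value of < 0.049". The next sentence turns this into a decision: "We will declare current steering DBS to be clinically superior to conventional therapy based on patient preference if 20 or more patients meet this criterion". The sentence after that speaks of steering being preferred by fewer than 20 participants.

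Just before this, the SA 2.3 primary analysis is given as a mixed model with the three programming strategies "as factor and patient preference and changes in PDQ-39 and UPDRS part 3 as data". So the same three outcomes appear in both the count rule and the primary model. Two of the three strategies are current steering; the third is conventional DBS.

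Protocol section 16a says how preference is collected: in an exit interview, patients are asked "to rank the programming strategies from the crossover study from best to worst". Neither document says how that ranking becomes a vote. Neither gives an order of testing, an any-or-all rule, a composite definition or a multiplicity adjustment for the three outcomes.

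**The concern.** One threshold and one p value are set beside three outcomes. A binomial tail describes one count, so the stated figure cannot describe all three unless the plan says how they combine. The declaration sentence mentions preference but then refers back to a criterion, and the only criterion defined is the sentence that lists all three.

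The rule carries weight. The SAP says it will declare clinical superiority on it, and the SA1 sample-size text says the overall sample of 30 is dictated by SA2.3. If the role of PDQ-39 and UPDRS part 3 stays open, it can be settled after the three counts are known, and the false-positive rate of the claim then depends on that choice. The p value also depends on two things the paragraph leaves unstated: whether the test is one-sided, and what chance of favouring steering counts as no effect.

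**Working it through.** **Inputs.** n = 30, threshold 20, three outcomes and p < 0.049 come from the SAP, Sample size for SA2. The three strategies, two of them steering, come from the SA 2.3 analysis text. The best-to-worst ranking comes from Protocol section 16a. The two-sided 0.05 level used for comparison comes from the SAP, Sample size for SA1. The documents give no correlation between the outcomes, so the correlations below are assumptions.

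**Step 1: reproduce the plan's figure.** With null probability 1/2,

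P(X ≥ 20) = Σ C(30, k) / 2^30 for k = 20 to 30 = 0.04937.

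- Doubled for a two-sided test: 2 × 0.04937 = 0.0987.
- Normal approximation: 0.0339 without continuity correction, z = (20 − 15)/√7.5; 0.0502 with it, z = (19.5 − 15)/√7.5.

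Of these, only the exact one-sided tail for a single count gives 0.049. Strictly, 0.04937 lies just above 0.049, so the less-than sign reflects rounding.

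**Step 2: error under each reading of the three-outcome rule.** Correlated cases were simulated: 200,000 trials per correlation, each with 30 participants and three latent normal outcomes sharing a common correlation. An outcome passes if 20 or more participants favour steering on it.

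| Reading | Chance of declaring superiority under the null |
|---|---|
| Vote alone decides | 4.9% |
| All three must reach 20 | at most 4.9%; 0.2% at correlation 0.5, 0.7% at 0.8, 1.2% at 0.9 |
| Any one of three suffices, independent | 1 − (1 − 0.0494)^3 = 14.1% |
| Any one suffices, correlation 0.4 | 12.9% |
| Any one suffices, correlation 0.7 | 11.8% |
| Any one suffices, correlation 0.8 | 11.1% |
| Any one suffices, correlation 0.9 | 9.9% |

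At correlation 1 the three counts are identical and the any-one figure falls back to 4.9%.

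**Step 3: sidedness.** At 21 of 30 the one-sided tail is 0.0214 and the two-sided value is 2 × 0.0214 = 0.043. At 20 of 30 the two-sided value is 0.0987. A two-sided 0.05 level, as in SA1, therefore needs 21.

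**Step 4: the null for the vote.** A null of 1/2 fits a choice between two options. Suppose instead that the vote is the top rank among three conditions that do not truly differ. Each is ranked first with probability 1/3, so a steering condition comes first with probability 2/3. The same holds if a participant counts whenever at least one steering condition outranks conventional DBS, since that fails only when conventional DBS is first. Then

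P(X ≥ 20 | n = 30, probability 2/3) = 0.585.

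Under that scoring the one-sided tail is 0.084 at 24 of 30 and first falls below 0.05 at 25 of 30 (0.035).

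**The case against.** The strongest reply is that the SAP does name the deciding outcome. The declaration is made on patient preference, the following sentence treats the threshold as a preference count, and the evidence sentence is introduced as patient-reported. On that reading there is one test at 4.9% one-sided, and PDQ-39 and UPDRS part 3 add no inflation. Other readings are also harmless. Requiring all three to pass can only lower the error. Classifying each participant once from the three measures gives a single count, still at 4.9% if the classification has a null of 1/2.

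Much of this stands. A reader might infer that the stated 0.049 is in fact a family error of 11% to 14%. The documents do not support that: they nowhere say that one outcome of the three is enough, and the declaration wording fits that reading least well. The range also rests on assumed correlations.

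The reply does not remove the ambiguity. If the vote alone decides, naming PDQ-39 and UPDRS part 3 in the binomial rule does nothing, yet they are named. UPDRS part 3 is a motor examination scored by observation, so the patient-reported label does not fit it. The primary mixed model lists the same three outcomes without an order, so it does not settle the matter. Nor does the feasibility setting excuse it, because the plan states a p value and a rule for declaring superiority. Finally, the vote-only reading still leaves sidedness and the null of 1/2 unstated.

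**Conclusion.** The point holds as an ambiguity in a decision rule, not as a demonstrated inflation. The stated p value is right, to rounding, for one count, one-sided, with a null of 1/2. The error of the declared claim is 4.9% if the vote alone decides, at most 4.9% if all three outcomes must pass, and about 10% to 14% if any one suffices. That last range assumes latent correlations from 0.9 down to 0.

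Even on the vote-only reading, which the wording favours, 0.049 needs two conditions that the SAP does not state: a one-sided test and a pairwise vote. The second matters more. Under a top-rank vote among three equal conditions, 20 or more would occur about 58% of the time with no true difference. Because the SAP does not define the scoring, that figure is conditional and is not a finding that the rule fails. The rule should be corrected in the SAP.

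**What to change.** Rewrite the decision paragraph under Sample size for SA2 as follows.

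1. Name the patient vote as the single confirmatory test and attach the p value to it only.
2. Take PDQ-39 and UPDRS part 3 out of the 20-of-30 rule. Test them with the planned Proc Mixed contrasts in fixed sequence, PDQ-39 and then UPDRS part 3, each only if the test before it passes. Alternatively, label both as supportive.
3. State that 0.049 is one-sided and that the two-sided value is 0.0987. If a two-sided 0.05 level is wanted, as in SA1, set the threshold at 21 of 30 (p = 0.043).
4. Define how the ranking becomes a vote, so that 1/2 is the right null: for example, whether one pre-named steering arm is ranked above conventional DBS. If a top rank among three is kept, use a null of 2/3 and reset the threshold.

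These choices should be fixed before outcomes are compared by condition. The cost is one SAP paragraph, with no change to visits, procedures or the planned 30. The downside is that no confirmatory claim on PDQ-39 or UPDRS part 3 is possible if the vote fails. A higher threshold would also lower power; the SAP gives no assumed preference rate from which to calculate by how much.
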